Ketamine is an analgesic agent and general anesthetic for human and veterinary use. It also has dissociative and psychedelic properties. For that reason, ketamine was categorized as a Schedule III drug in the Controlled Substance Act in August 1999. Over the past several decades, ketamine has been administered as an anesthetic to several million adults and children and has a very favorable safety profile. In addition, it has been used in psychophysiological studies in normal volunteers and patients with severe mental disorders including major depressive disorder and PTSD (with similar doses to those used in our proposed study) safely for three decades. Furthermore, the s-enantiomer of ketamine was approved for use as an adjunctive treatment for major depressive disorder by the Food & Drug Administration, and more recently for the treatment of depressive symptoms in individuals with major depressive disorder with acute suicidal ideation or behavior, reflecting its favorable risk versus benefit profile. Perceptual disturbances may manifest as vivid dreaming, visualization of psychedelic color, suspension in space, kaleidoscopic floating, and out-of-body experiences. Some patients report the psychic experiences as bizarre or frightening, while others describe them as pleasurable, joyful, or fascinating. When such reactions occur, they are usually mild and short-lived, resolving several minutes following the end of infusion. Other side effects commonly associated with ketamine include temporary increases in blood pressure and/or heart rate which will be monitored closely during, and for 1 hour after the end of, the infusions. Use of ketamine may also be associated with nausea. Interruption or discontinuation of infusion is usually adequate to resolve these ketamine-associated acute side effects.

Risks associated with WET:

Although WET may decrease PTSD and related symptoms, we recognize that individuals with PTSD may face the risk of symptomatic worsening. Indeed, one concern with exposure to trauma reminders is that individuals may acutely feel more anxious, even though exposure and habituation generally decrease PTSD symptoms over time. Conducting WET remotely via video telehealth requires special care in monitoring potential symptom worsening during sessions. We will take multiple precautions to ensure patient safety.

Financial risks:

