Secondary outcome measures (exploratory): The CAPS-5 will be administered weekly (beginning at baseline prior to the first ketamine infusion) until 6 weeks from the start of WET; thereafter, the CAPS-5 will be administered weekly as tolerated until 12 weeks; all participants will be administered the CAPS-5 at the 12-week time point. Participants who maintain PTSD symptom improvement after 12 weeks will be assessed monthly up to 24 weeks from the start of WET or until loss of improvement, by the blinded clinical rater. The PCL-5 and SDS (self-report scales), the MADRS (administered by the blinded clinical rater), and the CGI-S and CGI-Improvement scales (administered by a study psychiatrist or clinician) will be administered at the same time points until 12 weeks, and then monthly up to 24 weeks or until loss of improvement (See **3.1 Schedule of Activities**). The Quick Inventory of Depressive Symptomatology-Self-Report version (QIDS-SR)⁶⁶ and the Impact of Events Scale-Revised (IES-R),⁶⁷ both self-report scales, will be administered at baseline, 24 hours after the first infusion, at each infusion visit, and on the day of response to ketamine assessment, to capture any ketamine-related rapid changes in symptom levels. An abbreviated version of the Medical Outcomes Study Social Support Survey (MOS-SSS),⁶⁸ the Centrality of Event Scale (CES),⁶⁹ and the Perceived Ability to Cope with Trauma Scale (PACT)⁷⁰ will be administered at baseline (prior to any infusions) and again 3 weeks after the first WET session; data from these scales will be used for Aim-3 analyses.

Safety Assessments: Participants will be evaluated prior to each infusion by the PI or another study-affiliated psychiatrist; including review of vital signs, weight/BMI, drug and pregnancy tests, concomitant medications and adverse events. Participants will be monitored continuously during all ketamine infusions. On infusion days, side effects will be assessed with the Patient-Rated Inventory of Side Effects (PRISE) Adverse Event Visit Checklist,⁷¹ the Clinician-Administered Dissociative States Scale (CADSS),⁷² the Brief Psychiatric Rating Scale (BPRS) 4 items assessing positive symptoms,⁷³ and the Young Mania Rating Scale first item.⁷⁴

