5.2 EXCLUSION CRITERIA

EXCLUSION

1. Women who plan to become pregnant, are pregnant or are breast-feeding (because the medical risk of using ketamine during pregnancy and breast-feeding is unknown);
2. Serious, unstable medical illnesses such as hepatic, renal, gastroenterologic, respiratory, cardiovascular, endocrinologic, neurologic, immunologic, or hematologic disease, including gastro-esophageal reflux disease, obstructive sleep apnea, history of difficulty with airway management during previous anesthetics, ischemic heart disease and uncontrolled hypertension, and history of severe head injury;
3. Clinically significant abnormal findings of laboratory parameters, physical examination, or ECG;
4. Renal impairment, as reflected by a BUN >20 mg/dL, and/or creatinin clearance of >1.3 mg/dL;
5. Clinically significant uncorrected hypothyroidism or hyperthyroidism, as indicated by a TSH value 25% above or below the normal range;
6. A Body Mass Index (BMI) >40 ;
7. Hormonal treatment (e.g., estrogen) started in the 3 months prior to the first infusion day;
8. History of a neurodevelopmental disorder (e.g., autism, pervasive developmental disorder) ;
9. History of one or more seizures without a clear and resolved etiology;
10. Lifetime history of bipolar I or II disorder;
11. Presence of psychotic symptoms, or diagnosis of a lifetime psychotic disorder including schizophrenia or schizoaffective disorder;
12. Drug or alcohol use disorder within the preceding 3 months;
13. Previous recreational use of ketamine or PCP on more than one occasion, or any recreational use of ketamine or PCP within the last two years;

14. Previous non-response to clinical or research ketamine or esketamine administration;
15. Current diagnosis of bulimia nervosa or anorexia nervosa;
16. Patients judged clinically to be at serious and imminent suicidal or homicidal risk;
17. SBP >165 and DBP >95 at infusion days – higher BP allowed to account for stress or anxiety;
18. Concurrent treatment with opioid medication, or with long-acting or daytime short-acting benzodiazepines within two weeks of study start;*
19. Current cognitive impairment, as defined by a score <23 on the Montreal Cognitive Assessment (MoCA);
20. Estimated IQ <80;
21. Currently receiving evidence-based psychotherapy for PTSD (e.g., prolonged exposure, cognitive processing therapy);

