6.1.2 DOSING AND ADMINISTRATION

Ketamine:

The dose of ketamine at each infusion is fixed at 0.5mg/kg mg, and up to 60 mg per infusion (regardless of body weight), to be administered intravenously over 40 minutes. Individuals at or above 120 kg will receive 60 mg over 40 minutes. Ketamine infusion will be discontinued earlier if necessary due to side effects as described below:

1. Changes in psychiatric symptoms at any time during the study:
 - a. Treatment-emergent mania, hypomania, worsening suicidality or psychosis
2. Emergent medical symptoms on the infusion days:
 - a. Criteria for stopping the infusion:
 - i. Any change in mental status resulting in inability to respond to verbal stimuli.
 - ii. Severe headache, or severe anxiety, or other patient tolerability issues
 - iii. SBP >180, DBP >110 on 2 consecutive readings, ~5 min apart
 - iv. HR >120 for 5 minutes
 - v. RR< 6, SPO2 <90% at any time point
 - vi. Should the patient's vital signs deviate from normal, the clinician may temporarily pause the infusion until the vital signs/mental status have returned to normal, and subsequently resume the infusion at the same or slower rate. Recommended protocol: If 150 ml/h not tolerated, slow to 100 ml/h; If 100 ml/h not tolerated, slow to 50 ml/h.
 - b. During intravenous infusion day and post-administration monitoring period: in the event of tachycardia >110 beats per minute, systolic BP>160 mm Hg or diastolic BP>100mg Hg that is not resolved by pausing or slowing the rate of infusion, the study physician will treat using the following preferred medications:
 - i. Esmolol 100-500 mcg/kg IV titrated to reduce the heart rate and systolic BP.
 - ii. Nitroglycerin 20-80 mcg IV titrated to reduce the BP to an acceptable range.
 - iii. Further therapy with longer acting agents such as metoprolol, esmolol and labetalol will be administered if the response to initial therapy is not adequate.
 - c. If three consecutive vital sign measurements (over 15 minutes) are consistently above the HR and BP limits stated above despite therapy, intravenous infusion will be discontinued.
 - d. If a patient becomes sedated to the point that he/she is unresponsive to verbal commands or there is complete or partial airway obstruction, intravenous infusion will be discontinued. The patient would then be transferred to the Post Anesthesia Care Unit or an intensive care unit bed as necessary for further observation and treatment.

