- e. In the event that $\text{SpO}_2 < 95\%$ over 5-minute interval, the study physician will have the option of inserting a nasal cannula or adjusting the flow rate. If the SpO_2 does not increase to 95% or greater with intervention, the study will be discontinued and further therapy will be administered by the study physician.
- f. In the event of a respiratory or cardiac arrest, Team 7000 will be called.

Procedures Related to Ketamine Administration:

Ketamine Infusion: All infusion procedures and monitoring will take place at the Psychiatry Infusion Suite, Icahn School of Medicine at Mount Sinai (ISMMS), using the existing Standard Operating Procedures that are in place for the administration of ketamine in research studies. All eligible participants will receive **six infusions**, administered three times per week over two consecutive weeks. At each infusion, participants will receive 0.5 mg/kg racemic ketamine hydrochloride, the same dose administered in prior studies of ketamine for the treatment of PTSD.^{6,49} An indwelling catheter will be placed in the antecubital vein of the non-dominant arm, and pulse, blood pressure, digital pulse-oximetry, and ECG monitoring will be instituted. All physiologic monitoring data will be recorded on a standard anesthesia record beginning five minutes prior to ketamine administration. Co-Investigator [name] or another study- affiliated physician with privileges to administer ketamine will be present at the Psychiatry Infusion Suite throughout the administration of ketamine so that potential adverse events can be evaluated and treated promptly. A medical crash cart is available for emergencies. [name] or another study-affiliated physician will remain available until at least one hour following the termination of the study drug infusion or until the patient meets Aldrete criteria (good respiration, O₂ saturation, consciousness, circulation, and activity) for post- anesthesia care, whichever period is longer. Blood samples will be collected from participants during the first infusion for measurement of plasma ketamine and norketamine levels.

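### Exclusion criterion 17, the protocol's only numeric pre-infusion blood-pressure limit, joins its two limits with *and* and sets the systolic limit above the treatment limit in Section 6.1.2

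*Combined protocol and SAP*

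**What the plan says.** Section 5.2, criterion 17 excludes on "SBP >165 and DBP >95 at infusion days", with the explanation "higher BP allowed to account for stress or anxiety". Criterion 2 in the same list bars uncontrolled hypertension as an illness but gives no reading.

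Section 6.1.2 then sets three blood-pressure rules for the infusion itself:

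- Item 2.a.iii, a criterion for stopping: "SBP >180, DBP >110 on 2 consecutive readings", about five minutes apart.
- Item 2.b, covering the infusion day and the monitoring afterwards: the physician treats, with IV esmolol or nitroglycerin among the preferred drugs, for "tachycardia >110 beats per minute, systolic BP>160 mm Hg or diastolic BP>100mg Hg that is not resolved by pausing or slowing" the infusion.
- Item 2.c: if three consecutive measurements over 15 minutes are "consistently above the HR and BP limits stated above despite therapy, intravenous infusion will be discontinued".

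Section 2.3.1 warns of the expected direction of change: "Other side effects commonly associated with ketamine include temporary increases in blood pressure and/or heart rate". Section 4.1 provides the occasion on which a start limit would be applied: "Participants will be evaluated prior to each infusion by the PI or another study-affiliated psychiatrist; including review of vital signs".

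**The concern.** A start limit and an in-infusion treatment limit that apply on the same day should be in order: nobody should begin an infusion above the pressure at which the protocol wants treatment considered. This matters more with a drug expected to raise blood pressure. Here the order is reversed for systolic pressure, and the conjunction removes most of the force of the start limit.

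What is at stake is participant safety and clean conduct. A participant could begin an infusion with one pressure far above the intended limit. Another could receive an IV antihypertensive, or lose the rest of an infusion, for a pressure no higher than the one recorded before the drug was started. Each participant faces the check up to six times.

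**Working it through.** The plan states no figure to reproduce; the check compares the written limits with one another.

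**Inputs**

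- Criterion 17 as worded: excluded if SBP >165 and DBP >95.
- Criterion 17 read as *or*: excluded if SBP >165 or DBP >95.
- Item 2.b: SBP >160 or DBP >100. Item 2.c is read as using the same limits, because it follows 2.b directly and speaks of persistence despite therapy.
- Item 2.a.iii: SBP >180, DBP >110. The comma is undefined, so both *either* and *both* are tried.

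**Example pressures**

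| SBP/DBP | Criterion 17 as worded | Criterion 17 as *or* | Above 2.b | Above 2.a.iii (either) | Above 2.a.iii (both) |
|---|---|---|---|---|---|
| 160/95 | not excluded | not excluded | no | no | no |
| 163/90 | not excluded | not excluded | yes | no | no |
| 165/95 | not excluded | not excluded | yes | no | no |
| 166/96 | excluded | excluded | yes | no | no |
| 185/90 | not excluded | excluded | yes | yes | no |
| 160/112 | not excluded | excluded | yes | yes | no |
| 185/115 | excluded | excluded | yes | yes | yes |

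**Overlap with 2.b**

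- As worded, there is no upper SBP limit when DBP is 95 or less, and no upper DBP limit when SBP is 165 or less. The criterion excludes 166/96 but not 185/90.
- Read as *or*, the values that pass criterion 17 and exceed 2.b are SBP 161, 162, 163, 164 and 165 with DBP 95 or less. The band is 165 − 160 = 5 mmHg. There is no diastolic overlap, since 95 is below 100.

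**Overlap with 2.a.iii**

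- Criterion 17 as worded, comma as *either*: overlap from SBP 181 (DBP 95 or less) and from DBP 111 (SBP 165 or less).
- Criterion 17 as worded, comma as *both*: none. A pair above 180 and above 110 is also above 165 and above 95, so it is excluded.
- Criterion 17 as *or*: none on either reading of the comma, since every pair that passes has SBP at most 165 and DBP at most 95.

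**What follows during an infusion.** Take 163/90 before the start, unchanged afterwards. It is above 160. If pausing or slowing does not bring it down, item 2.b calls for IV treatment. If three readings over 15 minutes stay above 160 despite that treatment, item 2.c calls for discontinuation. No rise from the starting value is needed.

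**Checking the repair.** Changing only *and* to *or* removes the 2.a.iii overlap but leaves SBP 161–165. Lowering the systolic limit to 160 as well means that every pair that passes has SBP at most 160 and DBP at most 95, so none exceeds 2.b.

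**The case against.** A reader might infer that the protocol lets infusions start at pressures where treatment, discontinuation or stopping is already required. The documents do not support that. Item 2.b asks for drugs only after pausing or slowing has failed, item 2.c needs three readings despite therapy, and item 2.a.iii needs two readings. A starting reading alone meets none of them, and a reading raised by anxiety may settle. The stopping-rule overlap also appears in only one of the four combinations of readings: the literal *and* in criterion 17 with the comma in 2.a.iii taken as *either*. That reading of the comma is natural, because item 2.a.v lists respiratory rate and oxygen saturation the same way, but it remains a reading.

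Item 2.c is open to interpretation too. If its limits were taken to be those of 2.a, the 163/90 example would end at treatment.

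Failing to meet an exclusion criterion does not authorise a start. Vital signs are reviewed before each infusion, a physician with ketamine privileges is present, and infusions are run "using the existing Standard Operating Procedures that are in place for the administration of ketamine in research studies". Those procedures are not in the documents and may hold a tighter limit. Section 5.2 criterion 3 and Section 7.2 give further room for judgement.

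The lenient systolic value is also deliberate. The stated allowance for stress explains 165, but it was not carried into 2.b and does not explain the *and*. The other safeguards set no number. They lower the practical risk and leave the written limit as it is.

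**Conclusion.** The point holds, at minor severity, as a statement about the protocol text.

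- The systolic inversion of 5 mmHg (SBP 161–165 against the 2.b limit of 160) is present on either reading of criterion 17.
- The larger gap, in which one pressure may be arbitrarily high, rests on the literal *and*. Its extension to 2.a.iii also requires the comma to mean *either*.
- Reaching discontinuation under 2.c assumes that the pressure persists through pausing or slowing and then therapy, and that 2.c refers to the 2.b limits.

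The documents give no distribution of pre-infusion blood pressure, so the number of participants affected cannot be computed. The primary analysis, the other planned analyses and the sample-size statement do not depend on these limits.

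**What to change.** Reword criterion 17 as: *SBP >160 or DBP >95 before an infusion (recheck after rest; reschedule if still above)*.

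The *or* closes the one-pressure gap, and 160 matches the item 2.b systolic limit. The recheck keeps the sponsor's allowance for stress or anxiety in a safer form. It also makes clear that a single high reading does not exclude someone from the study, which is useful because Section 7.2 permits withdrawal when an exclusion criterion is met.

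The limit in 2.b should not be raised to 165 to make the numbers agree, since that would delay treatment during the infusion.

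The cost is the wording of one criterion, with no extra data or participants. An occasional participant at SBP 161–165, or with only one limit exceeded, would wait or be rescheduled. The edit removes the inversion but leaves no systolic margin: someone starting at 160 passes the 2.b number after a rise of 1 mmHg, and item 2.b then applies as intended.

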5.3 LIFESTYLE CONSIDERATIONS

During this study, participants are asked to:

- Participants will be asked to refrain from eating anything or drinking any non-clear liquids starting at midnight the night before each infusion.
- Inform the study team of any changes in their medications or psychotherapy regimen.
- Refrain from taking short-acting benzodiazepines during daytime.
- Participants who use tobacco products will be instructed that use of nicotine-containing products (including nicotine patches) will not be permitted while they are in the clinical unit.

5.4 SCREEN FAILURES

Screen failures are defined as participants who consent to participate in the clinical trial but are not subsequently assigned to the study intervention or entered in the study. A minimal set of screen failure information is required to ensure transparent reporting of screen failure participants, to meet the Consolidated Standards of Reporting Trials (CONSORT) publishing requirements and to respond to queries from regulatory authorities. Minimal information includes demography, screen failure details, eligibility criteria, and any serious adverse event (SAE).

Individuals who do not meet the criteria for participation in this trial (screen failure) because of an exclusionary concomitant medication, or a recent change in medications or psychotherapy may be rescreened. Rescreened participants should be assigned the same participant number as for the initial screening.

5.5 STRATEGIES FOR RECRUITMENT AND RETENTION

Planned Recruitment Activities:

The research strategy for the present study calls for the enrollment of N=30 adults with chronic posttraumatic stress disorder (PTSD), aged 18-70 years. This enrollment is with the goal of identifying up to N=16 participants who are screened, eligible, and go on to receive ketamine infusions and WET. This is based on an anticipated screen fail rate of 25% to 50%. This enrollment will take place over the proposed 54-month recruitment period.

The expected enrollment rate of ~1.2 subjects per month who receive ketamine infusions is highly feasible based on the current flow of subjects in clinical trials at the Depression and Anxiety Center for Discovery and Treatment (DAC) and the demonstrated track record of similar rates in prior studies at DAC and recruiting from WTC populations in CDC/NIOSH-funded studies led by PI [name]. As one of the major research and clinical programs at the Department of Psychiatry at the Icahn School of Medicine at Mount Sinai (ISMMS), DAC has five full-time faculty members. This includes three psychiatrists, two part-time clinical psychologists, two full-time post-doctoral fellows, three full-time Masters-level clinical raters, five full-time clinical research coordinators, a database manager, and a program administrator. Investigators at DAC have a long track record in successfully recruiting subjects and completing studies involving the assessment and treatment of individuals with PTSD.

Recruitment Procedures:

We will post advertisements on Craigslist, ResearchMatch, Facebook, TrialFacts, BuildClinical and Google and will post flyers in the community, and accept referrals from clinicians. Through TrialFacts and BuildClinical, we will have targeted advertisements on Google and Facebook.

Potentially eligible participants who express interest in being considered for this clinical trial will complete a phone screen interview under the supervision of PI [name]. The PI will review subject enrollment at weekly project meetings with the primary study coordinator and Co-Investigators Drs. [name] and [name], so that any deviation from the anticipated enrollment schedule will be detected and remedied quickly. All outreach and advertising activities will also be reviewed on a weekly basis.

Engagement Strategies for Retention:

The PI will hold weekly project meetings with the study coordinator and Co-Investigators Drs. [name] and [name] to monitor enrollment and ensure that enrolled subjects are completing all study procedures as per protocol.

For infrastructure, the Scientific Computing department at ISMMS provides a secure centralized electronic data management platform that is HIPAA and FDA-compliant – Research Electronic Data Capture (REDCap). For this specific project, we will create databases in REDCap for screening, subject tracking, and a study database proper. As subjects complete study visits, the date of each visit will be entered in the database. Missed visits will be coded for reason (such as scheduling issues, illness). On a weekly basis, the primary research coordinator, who will also serve as data manager, will run a report on patient enrollment and study progress for review by the PI. On an ongoing basis, the data manager, PI,

and Co-Investigators Drs. [name] and [name] will review the status of patient accrual and retention, as well as study case report form completion, to identify and resolve bottlenecks or problem areas that arise. [name] will additionally meet regularly with the study therapists, and work together with [name] (who will supervise the study therapists) to identify any potential issues related to delivery of WET to participants.

Within DAC, the study coordinator will be the participant's point of contact during the study. Subjects will be provided with phone and email contact information for their coordinator, in addition to contact information for the PI. When enrolled, participants will provide detailed contact information for themselves, their clinical providers (if applicable), and a family member or close friend who is aware of the participant's study participation. At each visit, the study coordinator will "check in" with the participant regarding protocol adherence and study satisfaction, in addition to any protocol-specific procedures. This system provides an opportunity to detect reasons for non-adherence or early discontinuation in a timely fashion and to address any issues, if at all possible.

Strategies to ensure a diverse, representative sample:

Since its inception, ISMMS has fostered community partnerships that are mutually beneficial to the School and nearby underserved populations. Faculty members have benefited from collaborations with underserved and often hard-to-reach populations and front-line clinicians, to recruit for research, develop research partnerships and to ensure that community expertise, experiences and priorities inform their work. The Centers for Community and Academic Research Partnerships (CCARP) at Mount Sinai is facilitating the formation and transformation of these partnerships so that they become the catalyst for groundbreaking research that uncovers and addresses important social, environmental, and health problems; builds skills among academic and community partners; and improves health of communities.

The ISMMS is part of a large urban medical center, located in the Manhattan borough of New York City, and benefits from a large and diverse catchment area. For the proposed clinical trial there are no special restrictions with regard to ethnicity or race. It is expected that the study sample will closely approximate the racial and ethnic composition of populations residing in the New York City metropolitan area.

Potential recruitment/enrollment challenges and strategies that can be implemented in the event of enrollment shortfalls:

Anticipated barriers include issues with staff workload and scheduling windows. This will be addressed by the use of back-up coordinators for the primary study coordinator on the proposed project. Furthermore, Co-Investigators [name], [name], and [name] will serve as back-up study physicians for the PI, [name], within the research team. Back-up team members will allow the team to screen and enroll participants and complete study visits within participant's availability. All study staff involved in participant recruitment will be trained by the PI, in collaboration with Director of DAC [name], and participant progress and study procedures will be reviewed at weekly project meetings to ensure protocol adherence and consistency of procedures across primary and back-up study personnel.

Anticipated participant-related barriers include appointment scheduling, transportation issues, and maintaining contact between study visits. To ensure that participants are able to attend appointments,

the visit schedule will allow for flexibility. To help address transportation issues, the study team will offer patients metro cards and other transportation resources available through DAC, including a car service to take participants home on the days of their ketamine infusions. Research staff will discuss contact methods with each participant during screening in order to establish multiple methods of contact, along with preferred contact methods to maintain contact between appointments. Research staff will check voicemail and email daily in order to be able to respond to patient contact. Staff will also reach out before each scheduled appointment to ensure participants are able to attend and complete visits as scheduled. To ease the burden on participants, we will also administer the five WET sessions remotely, via a HIPAA-compliant video telehealth platform.

At the current moment, the COVID-19 pandemic poses a potential barrier to enrollment in this and other studies. DAC is working closely with Departmental and Health System leadership to ensure optimization of SOPs related to mitigating risks pertaining to COVID-19 infection. Strategies to mitigate this barrier include the use of clear and consistent messaging to potential participants regarding safety precautions at DAC, including the implementation of thorough and consistent hospital-grade cleaning and disinfecting, the use of masks and eye protection by study personnel, the use of masks by participants, and social distancing. We are also allowing provisions for remote visits (via HIPAA-compliant video telehealth platforms) wherever possible, in addition to the WET sessions, which will take place remotely.

In the case of slower than anticipated enrollment, PI [name] and Co-Is Drs. [name] and [name] will review reasons for pre-screen and screen failures during weekly DAC research meetings, and consider additional recruitment and outreach methods including additional advertising methods, and additional outreach methods to clinicians and centers providing treatment to individuals with chronic PTSD.

